7.5 Study Scheme Diagram

8. STUDY PROCEDURES

8.1 Recruitment

Participants will be enrolled via adverts posted at each of the three QMUL campuses and social media. No one with direct connections to the management or supervision of this study or any their collaborators will be eligible for recruitment. For QMUL student recruitment, permission from the Deanery will also be sought. Adverts will also be posted on social media such as Facebook and Twitter as well as newspapers. A PDF copy of the poster will be added to the William Harvey website.

Potential participants will be asked to contact the research team via email or over the phone. Then they will be invited to attend screening thereafter.

All potential participants will be given the Participant Information Sheet (PIS) by a member of the study team which they can take away for consideration. The participant will be given at least 48 hours to decide whether or not to take part in the study following being given the PIS.

All participants who demonstrate interest in enrolling will be invited to attend the William Harvey Clinical Research Centre (CRC) one week later where they will have the opportunity pose any questions to the research team and then will have the opportunity to formally enrol.

Up to a maximum payment of £400 will be organised for participation in the study to reimburse London travel expenses within Greater London.

8.2 Screening and Consent

The consenting procedure will follow the William Harvey Heart Centre, Clinical Research Centre's SOP 011.

The doctors obtaining informed consent will have current GCP training. They will be familiar with the study, the fish oil supplement and will use the current version of the Patient Information Sheet (PIS) and Consent Form, which has been approved by ethics.

The doctors obtaining consent will ensure that the participant is able to understand the information given and will explain the nature, purpose, procedures, risks and benefits of the study to the participant. The doctor will answer any questions the participant may have to the participant's satisfaction. The participant will be given at least 48 hours to decide whether or not to take part in the study following being given the PIS. The date the PIS is given to the participant will be documented to ensure that sufficient time is given for consideration.

The doctor will explain the consent form and obtain the participant's initials and dated signature on the consent form. They will then countersign and date the consent form after the participant has signed it. The original signed consent and PIS will be kept in the subject record in the CRC, a copy will be filed in the Site Investigator File and the participant given a copy.

Volunteers will also be asked, on the patient information sheet, if they are willing to have their RNA extracted and stored for subsequent analysis, on the understanding that they will not be informed of any genetic information, and that the team dealing with them in the trials unit will also never be made aware of any genotyping information. These samples will be stored for a maximum of 2 years. These samples will be used to investigate the expression of SPM biosynthetic enzymes, the SPM receptors and pathways that these molecules may activate.

Basic screening will be performed, which will include- clinical history taking, vital signs- Blood pressure, pulse rate, ECG, physical examination and blood tests; full blood count, biochemistry, liver function tests, glucose and C reactive protein. The identity of healthy volunteers will be documented by taking a photocopy of an original photo ID card (passport, driving license, TFL photocard), and archived with the study records. Before each dosing the identity of the volunteers will be confirmed against the identity records on file.

8.3 Intervention

After determining eligibility participants will be randomly assigned to one of the eight groups outlined in the table below where each participant will receive all three doses and the placebo but in a different sequence to minimise any interaction effects.

In order to ensure adequate recruitment into all eight cycles prior to interim analysis group allocation will be divided into two blocks with 20 volunteers per block. Each of the supplement capsule contains 1.5g of essential fatty acids. So administration of 1 supplement capsule and 2 placebo capsules will deliver 1.5g of omega-3 fatty acids, administration of 2 supplement capsules and 1 placebo capsule will deliver 3 g of omega-3 essential fatty acids and administration of 3 supplement capsule will deliver 4.5g essential fatty acids.

Group	Treatment			
	Cycle 1	Cycle 2	Cycle 3	Cycle 4
Group 1	3 capsules Placebo	1 capsules Supplement & 2 capsules Placebo	2 capsules Supplement & 1 capsules Placebo	3 capsules Supplement
Group 2	1 capsules Supplement & 2 capsules Placebo	2 capsules Supplement & 1 capsules Placebo	3 capsules Supplement	3 capsules Placebo
Group 3	2 capsules Supplement & 1 doses Placebo	3 capsules Supplement	3 capsules Placebo	1 capsules Supplement & 2 capsules Placebo
Group 4	3 capsules Supplement	3 capsules Placebo	1 capsules Supplement & 2 capsules Placebo	2 capsules Supplement & 1 capsules Placebo
Group 5	3 capsules Supplement	2 capsules Supplement & 1 capsules Placebo	1 capsules IMP & 2 capsules Placebo	3 capsules Placebo
Group 6	2 capsules Supplement & 1 capsules Placebo	1 capsules Supplement & 2 capsules Placebo	3 capsules Placebo	3 capsules Supplement
Group 7	1 capsules Supplement & 2 capsules Placebo	3 capsules Placebo	3 capsules Supplement	2 capsules Supplement & 1 capsules Placebo
Group 8	3 capsules Placebo	3 capsules Supplement	2 capsules Supplement & 1 capsules Placebo	1 capsules Supplement & 2 capsules Placebo

This above protocol will be followed until all forty participants are recruited (unless halted after the interim analysis).

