7.4 Study Design / Plan – Study Visits

This is an open label double-blind, placebo controlled, crossover study that aims to determine the dose of omega-3 fatty acids that leads to an increase in peripheral blood SPM levels and the kinetics of this regulation.

- Each participant will give a baseline blood sample then they will be given one of the randomly allocated three doses of fish oil supplement, or a matching placebo in one of 8 study groups [this will be on a 1:1:1:1:1:1:1:1 ratio]. Blood will be collected again at 2h, 4h, 6h and 24h after supplementation/placebo.

- This design allows to compare the levels of SPM pre and post supplementation and therefore to account for inter participant variation in circulating SPM levels as well as for any differences in white blood cell responses *ex vivo*.

- Using a crossover design and a placebo, diurnal variation in the levels of SPM (currently not known) will be checked. In addition, using each volunteer as their own control for comparison with each dose of supplement will further improve the power of the study.

- Each participant is expected to be involved in the study for a maximum of 11 weeks from initial consent and screening.

- Participants will be asked to refrain from consuming caffeine containing drinks at least 2h prior to their visit.

- Participants will be expected to refrain from alcohol intake for at least 24h before screening for the study, and for at least 24h before each cycle of the study.

- Participants will also be asked not to take other supplements, medications for the duration of the study, and to avoid fish containing meals for 2 days before each study cycle.

- For each cycle, the participants will make two visits, the first visit will be of a maximum of 8hrs. Here baseline (0hrs) blood sample will be obtained and the supplement/placebo given.

- Blood will be collected 2hrs, 4hrs and 6hrs following supplement/placebo intake and the participant will be free to leave after the 6hrs blood collection.

- During this time participants will be asked to refrain from drinking caffeine containing drinks such as coffee or tea.

- Participants will then be asked to return the next day (24h after fish oil supplement/placebo intake).

[figure not shown]
- The 24h blood draw should take a maximum of 30 min.

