- After a minimum of 48 hours, and not more than two weeks participants will be asked to return, their eligibility criteria re-assessed and then administered the next supplement/placebo dose in the cycle as determined by the group they were assigned to at the beginning of the study (see Section 13.5.1)

- A first follow-up phone-call to the volunteer will be made to check well-being at 2 weeks (+/- 1 week) after the end of the volunteers last cycle
 - A Second follow-up phone-call to the volunteer will be made to check well-being at 4 weeks (+/- 1 week) after the end of the volunteers last cycle
 - If any adverse effects are reported by the volunteer they will be asked return for further evaluation.

The fish oil supplements that will be used in the present studies are isolated from Peruvian anchovies. These are then packaged as emulsions and supplied by Metagenics with whom we will have contractual agreement in place before the start of the study. Metagenics will also supply the emulsion that does not contain fish oil supplements to be used as placebo. Both of these products are not considered to be drugs or medicines and classified as foodstuffs.

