8.4 Randomisation Process

Patients will be block randomised on a 1:1:1:1:1:1:1:1 basis to receive either one of the three doses of fish oil or placebo in one of 8 study groups, using a binary random number sequence (www.random.org).

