8.8 Clinical Protocol

At least 24h prior to consent, participants will be provided an information sheet by an appropriate method including email, post or by attending the clinic, detailing the rationale and hypothesis of the study and on attending the screening visit the study physician will address any questions that the participants may have. They will be asked to sign the informed consent and then their eligibility criteria will be assessed based on the inclusion criteria set out for the study. Basic observations, blood pressure, pulse, resting supine ECG, Blood samples for full blood count, biochemistry and glucose and CRP, then a physical examination will be performed.

Volunteers passing screening will then:

- Will give a baseline blood sample (12ml)
- Be given one of the randomly allocated three doses of fish oil supplement, or a matching placebo [this will be on a 1:1:1:1 ratio].
- Give blood (12ml/time interval) will be collected again at 2h, 4h, 6h
- Be allowed to leave and they will be asked to return the following day for the collection of the 24h blood sample.
- Be asked to return after a minimum of 48h but no later than 2 weeks
- Identity will be verified
- Blood will be obtained (12ml)
- Be given the next supplement dose/placebo that is listed on their assigned study group and the injection witnessed by a member of the study team.
- Blood will be obtained after 2h, 4h and 6h.
- Be free to leave and will be asked to return after 23h from supplementation
- The 24h blood sample will be collected and the participants will be asked to return again after a minimum of 48h and no later than 2 weeks for their next supplement dose/placebo cycle
- Identity will be verified
- Blood will be collected (12ml)
- Supplement/placebo will be administered and ingestion witnessed.
- Blood will be collected at the same intervals outlined above
- Participants will be asked to return for the last supplement dose/placebo listed on their study group at least 48h after the last blood donation (24h blood sample) but no later than 2 weeks.
- Essentially the same protocol outlined above will be followed for the last cycle.
- A first follow-up phone-call to the volunteer will be made to check well-being at 2 weeks (+/- 1 week) after the end of the volunteers last cycle
- A Second follow-up phone-call to the volunteer will be made to check well-being at 4 weeks (+/- 1 week) after the end of the volunteers last cycle

Participants can withdraw from the study at any time.

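### Minor: blocks of 20 cannot hold an equal ratio over eight groups, and the eight printed sequences use only 8 of the 12 possible treatment transitions

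*Combined protocol and SAP*

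**What the plan says.** **Allocation.** Section 8.3 sets the block structure: "group allocation will be divided into two blocks with 20 volunteers per block". The purpose it gives for this is as follows: "In order to ensure adequate recruitment into all eight cycles prior to interim analysis". The table in that section has eight groups and four cycles. Section 8.4 says "Patients will be block randomised on a 1:1:1:1:1:1:1:1 basis", and Section 7.4 has treatment given "in one of 8 study groups [this will be on a 1:1:1:1:1:1:1:1 ratio". The total is 40. No section says how a block of 20 is to be spread over eight groups.

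**Sequences.** Section 8.3 explains the different orders: "each participant will receive all three doses and the placebo but in a different sequence to minimise any interaction effects". With P for placebo and 1, 2, 3 for the number of supplement capsules (1.5, 3.0, 4.5 g), Groups 1 to 8 are P123, 123P, 23P1, 3P12, 321P, 21P3, 1P32, P321. The single entry for Group 5 that says IMP is read as supplement.

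**Use of the data.** Section 9.4 tests each post-dose value against the same person's pre-dose value, and Section 7.4 takes a new 0h sample in each cycle. But 7.4 also counts on each volunteer serving as own control for comparison with every dose, and Section 9.3 picks the dose with the greatest change. Both uses compare results across cycles. Between cycles, 7.4 says: "After a minimum of 48 hours, and not more than two weeks participants will be asked to return".

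**The concern.** Whoever writes the allocation list must supply a rule that the protocol leaves out. A block described as equally allocated over eight groups cannot be so at size 20, and the first block appears to mark the interim analysis.

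The sequence table has a separate gap. The orders are meant to limit interaction between treatments. If a dose affects the response in the next cycle, what matters is which treatment precedes which. In the printed table each treatment is only ever preceded by two of the other three. Any carry-over would then fall unevenly on the treatments and could distort the comparison of doses on which the choice for future trials rests.

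**Working it through.** **1. Block size.** Inputs: block of 20, eight groups, equal ratio, total 40.

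- Per block: 20/8 = 2.5. The nearest split is four groups of 3 and four of 2.
- Whole trial: 40/8 = 5, so the ratio is attainable at the end, but it is guaranteed only if the groups with 3 in block 1 have 2 in block 2.

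Cost of imbalance, by least squares with participant, cycle and treatment, in units of the within-person variance sigma²:

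| | Balanced | Worst case |
|---|---|---|
| n = 20, all 70 possible 3/2 splits | 2/20 = 0.100 | 0.1021 |
| n = 40, all 1107 size patterns from two such splits | 2/40 = 0.050 | 0.0510 |

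Both worst cases are about 2% above balance.

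**2. Cycle balance and transitions.** Each treatment appears twice in each cycle, so the table is balanced by cycle. Group 5 reverses Group 1, Group 6 reverses Group 4, Group 7 reverses Group 3 and Group 8 reverses Group 2. Eight sequences with three transitions each give 24 transitions:

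- Present, three times each: P-1, 1-2, 2-3, 3-P, 3-2, 2-1, 1-P, P-3.
- Absent: P-2, 2-P, 1-3, 3-1.

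**3. Precision at n = 40.** Same model, with and without a first-order carry-over term. The carry-over model is full rank (49 of 49) for the printed table.

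| Contrast | No carry-over term, either layout | Carry-over term, printed | Carry-over term, Williams |
|---|---|---|---|
| P or 3.0 g versus 1.5 g or 4.5 g (four pairs) | 0.050 | 0.1625 | 0.055 |
| P versus 3.0 g; 1.5 g versus 4.5 g | 0.050 | 0.050 | 0.055 |

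For the four pairs the ratio is 0.1625/0.055 = 2.95 in variance, or about 1.7 in standard error.

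**4. Illustration of uneven distortion (assumed inputs).** Suppose carry-over equals lambda times the previous treatment's effect and is not modelled. Both layouts are balanced by cycle and every participant takes every treatment, so the estimate for a dose is its mean minus the placebo mean. Three of four cycles have a predecessor, so each treatment mean shifts by 0.75 × lambda × (mean effect of its predecessors).

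Assume true effects of 0, 1, 1.2, 1.25 for placebo, 1.5, 3.0, 4.5 g (a plateau) and lambda = +0.25, so 0.75 × 0.25 = 0.1875.

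Printed table:

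- Placebo and 3.0 g follow 1.5 or 4.5 g: shift 0.1875 × (1 + 1.25)/2 = 0.211.
- 1.5 and 4.5 g follow placebo or 3.0 g: shift 0.1875 × (0 + 1.2)/2 = 0.1125.
- Against placebo, 1.5 and 4.5 g lose 0.211 − 0.1125 = 0.098 and 3.0 g loses nothing. Estimates are 0.90, 1.20, 1.15, so the top two doses change places.

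Williams: each treatment follows the other three equally, so a dose with effect t loses 0.75 × lambda × t/3 = lambda × t/4 against placebo. Every effect is multiplied by 1 − 0.0625 = 0.9375, giving 0.94, 1.13, 1.17. The order is kept.

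With lambda = −0.25 the printed table gives 1.10, 1.20, 1.35 and Williams multiplies every effect by 1.0625. The order is kept in both, but the printed table widens the gap between the top two doses from 0.05 to 0.15.

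The reversal needs lambda above 0.05/(0.75 × 0.525) = 0.13 for these effects, where 0.525 = 1.125 − 0.6 is the difference between the two predecessor means. With linear effects 0, 1, 2, 3 the order survives at +0.25 in both layouts.

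**The case against.** **The ratio need not be exact in every block.** It is exact at 40 if each group reaches five, and a 3/2 split fills every group before the interim. This largely stands: the defect is a missing rule and not a threat to the result. Placing Groups 1-4 in block 1 and Groups 5-8 in block 2 makes the numbers fit, but it defeats the stated reason for the blocks.

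**Other apparent conflicts.** A reader might take Section 8.8's "or a matching placebo [this will be on a 1:1:1:1 ratio" as contradicting the eight-group ratio. It does not: it refers to the four treatments, and each treatment opens two of the eight groups. Nor do the weekly visits in Section 8.9 form a rival interval; they lie within the 48-hour to two-week window. Section 8.8 dates the last cycle "at least 48h after the last blood donation (24h blood sample) but no later than 2 weeks", and nothing in this point depends on that.

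**The plan makes no claim of carry-over balance.** Interaction effects are not defined in 8.3, the planned analysis has no carry-over term, and without one the printed table is as efficient as Williams. All of this is correct. It confines the second point to cross-cycle uses.

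**The sign of any bias is not fixed.** A residual still present at 0h is subtracted from the change. If it stays constant to the post-dose sample it cancels; if it has faded by then, lambda is negative. A positive lambda requires the earlier dose to raise the new response itself. This stands. It is why both signs are shown, and why no single bias figure should be quoted without saying which form is assumed.

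**Conclusion.** Minor, on both counts. The block size and the stated ratio do not fit together within a block, and the rule that would bring each group to five is missing. The cost is at most about 2% in variance, and no conclusion of the trial changes.

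The sequence table only partly serves its stated aim, because 4 of 12 transitions never occur. A reader might infer that the dose comparisons are biased or the planned tests invalid. The documents do not support that: they give no carry-over size, and the Wilcoxon tests compare values within a cycle against a fresh baseline. The 25% carry-over and the plateau are assumptions chosen to show a mechanism. What is established is narrower. Under proportional carry-over of either sign, a Williams layout rescales all dose effects by the same factor and keeps their order, whereas the printed table distorts them unevenly. The better layout costs no precision unless carry-over is modelled, so it is worth adopting while the list can still be changed.

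**What to change.** **Allocation (Sections 8.3 and 8.4).** Either write: *Participants will be randomised to the eight groups in five permuted blocks of 8, giving five per group*; or keep blocks of 20 and add: *Block 2 complements block 1, so that each group has five participants*. Change the reference to eight cycles in 8.3 to eight groups. With blocks of 8, an interim at 16 or 24 falls on a block boundary; one kept at 20 would still find two or three in every group. Cost: wording and a new pharmacy list.

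**Sequences (Section 8.3), before enrolment.** Replace the table with two Williams squares of the same four treatments: P132, 12P3, 231P, 3P21 and P123, 13P2, 321P, 2P31. Every transition then occurs twice, and each treatment appears twice per cycle. Alternatively use the first square alone. Its four sequences fit blocks of 20 exactly (5 per sequence, 10 at 40) with the same precision; the ratio in 7.4 and 8.4 would then become 1:1:1:1 over four groups, and the block wording above would not be needed.

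Cost: the same new list, issued once. Sample size, capsules, visits and the interval between cycles do not change. The only statistical price is 0.050 to 0.055 sigma² for two contrasts, and only if carry-over is modelled.

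**Optional (Section 9.4).** Add a sensitivity analysis of change from the same cycle's 0h value, with participant, cycle, treatment and previous-cycle treatment. It would need its mediators, time point and any transformation named in advance.

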8.4 Randomisation Process

Patients will be block randomised on a 1:1:1:1:1:1:1:1 basis to receive either one of the three doses of fish oil or placebo in one of 8 study groups, using a binary random number sequence (www.random.org).

8.5 Blinding Process

The study treatment will be prepared and labelled by the WHRI Heart Centre Pharmacy, according to the randomisation schedule. Active and placebo treatments will be labelled such that it is not possible to distinguish between them. Each subject's treatment will be given a unique code number, that is traceable to study group and batch numbers of placebo and supplement.

Investigators and research team including CI, PI, trial coordinator, research nurses and lab staff, will be blinded to the treatment being provided. A sealed copy of the randomisation code will be kept in a locked file in the WHRI Heart Centre Dispensary. The investigator will be supplied with sealed envelopes, each one containing the treatment allocation for the subject whose number appears on the outside of the envelope. Those envelopes will be kept in the study master file, readily accessible to clinical staff. Emergency procedures for revealing treatment codes are specified in Section 7.6 below. The investigator, sponsor's medical expert and clinical monitor will remain blinded throughout the study, unless safety concerns necessitate unblinding.

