9.3 Sample Size

Power calculations were conducted using data obtained from published studies where healthy volunteers were given 1 mg essentially (from a different source to that being investigated in the present study) and peripheral blood lipid mediator levels were evaluated pre-essential fatty acid and 4 hours after supplement intake (Colas et al Reference 17). Using pre and post values of 10 mediators values from these studies and Wilcoxon matched-pairs signed rank test a sample size of 33 participants is required to detect a threefold odds of an increase in post value when compared with the pre value with a power of 80% at the 5% level of statistical significance using the formulae from reference 18. Fifty mediators will be examined and it is recognized that at the 5% level of statistical significance around 2-3 mediators will falsely be identified as having significant changes. However the functional effect of all significant mediators will be subsequently examined by assessing white blood cell function, including the ability of peripheral white blood cells to phagocytose bacteria and the response of peripheral white blood cells and platelets to an inflammatory stimulus. If we do not observe increases in the ability of peripheral white blood cells to phagocytose bacteria and/or decreases in the activation of peripheral white blood cells and platelets then these mediators will be assumed to be false positive results. For these analysis the white blood cell function and peripheral blood lipid mediator levels at the 2h and 4h intervals post essential fatty acid/placebo administration will be compared to pre-supplementation values. The time point and dose that give the greatest change in all the mediators and the greatest regulation of peripheral white blood responses will be judged to be the main outcome measure for future trials.

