9.4 Statistical Analysis Plan

Wilcoxon matched-pairs signed rank test will be used to analyse the pre and post values of 10 mediators as well as white blood cell function (at 2 and 4h). The time point corresponding to the greatest number of the mediators being statistically significantly different from their pre-test values at the 5% level of statistical significance will be identified as the time point of interest. At the 5% level of significance testing 50 mediators will result in at least 2-3 associations being falsely statistically significant. Thus, the functional effect of all significant mediators will be subsequently examined by assessing white blood cell function, including the ability of peripheral white blood cells to phagocytose bacteria and the response of peripheral white blood cells and platelets to an inflammatory stimulus to determine if the identified associations are likely to be true changes. If we do not observe increases in the ability of peripheral white blood cells to phagocytose bacteria and/or decreases in the activation of peripheral white blood cells and platelets then these mediators will be assumed to be false positive results. Values at different times will not be compared just the value at each time point will be compared to the same person's pre test values.

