12.1 Confidentiality The Principal Investigator has a responsibility to ensure that participant anonymity is protected and maintained. They must also ensure that their identities are protected from any unauthorised parties. Information with regards to study participants will be kept confidential and managed in accordance with the Data Protection Act, NHS Caldicott Guardian, The Research Governance Framework for Health and Social Care and Research Ethics Committee Approval. All trial data will be stored in line with the Medicines for Human Use (Clinical Trials) Amended Regulations 2006 and the Data Protection Act and archived in line with the Medicines for Human Use (Clinical Trials) and all subsequent amendments as defined in the JRMO SOP 20 Archiving.

The Chief Investigator and the study team will adhere to these parameters to ensure that the Participant's identity is protected at every stage of their participation within the study. To ensure this is done accordingly, at time of consent each participant will be allocated a unique screening number by either the PI or a member of the study team before undergoing any screening procedures.

Personal information will be collected upon enrolment, this will be stored in accordance with QMUL Data Protection regulations.

In order to maintain confidentiality, participants will be identified by a unique trial identifier only. This number will be randomly generated and will be assigned to each participant. In addition to relating to the participant's dataset the code will also be associated with the specific study cycle that the participant is enrolled to.

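### The blind covers treatment only and no masking of draw time is described, yet every planned test compares a post-dose reading with a pre-dose reading

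*Combined protocol and SAP*

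**What the plan says.** **Blinding.** Section 8.5 lists the investigators and research team and states that "research nurses and lab staff, will be blinded to the treatment being provided". Draw time is not mentioned.

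**Tests.** Section 9.4 states that the "Wilcoxon matched-pairs signed rank test will be used to analyse the pre and post values of 10 mediators as well as white blood cell function". The draw times it names are 2 h and 4 h. The section ends: "Values at different times will not be compared just the value at each time point will be compared to the same person's pre test values". Section 9.3 says the same of cell function and mediators: "levels at the 2h and 4h intervals post essential fatty acid/placebo administration will be compared to pre-supplementation values". The sample size rests on this contrast too: "a sample size of 33 participants is required to detect a threefold odds of an increase in post value when compared with the pre value".

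**Sample identity.** Section 12.2 says that samples are coded, with the key held by the PI, and refers to a coding system in 14.3. Section 14.3 now deals with serious breaches. The only identifier described is in 12.1, where "the code will also be associated with the specific study cycle that the participant is enrolled to".

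**Laboratory work.** Section 8.7 has samples processed within an hour of collection under a laboratory manual. Plasma goes into methanol with deuterium-labelled standards, is stored at -80°C and is processed in batches of 20-24. Run order is not given.

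**The concern.** What is hidden is which capsules were swallowed. What is tested is whether a 2 h or 4 h sample differs from the 0 h sample. A reader who does not know the treatment but does know the draw time knows which side of the tested contrast each sample is on, and which way it is expected to move.

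Peak review and gate setting both involve judgement. A slight lean toward the hypothesis would enter the primary endpoint (more SPM) and both secondary endpoints (more phagocytosis, less activation). Sections 9.3 and 9.4 rely on the cell-function results to separate true mediator changes from chance ones. Those results are themselves pre/post cytometry readings, so the filter could lean the same way as the findings it is meant to screen.

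**Working it through.** **1. Is pre/post really the planned contrast?** The sample size supports this. Inputs from 9.3: threefold odds of an increase, 80% power, 5% level, N = 33.

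- P(increase) = 3/(1 + 3) = 0.75.
- Two-sided sign-test formula: n = (1.960 + 0.842)² / [4 × (0.75 - 0.5)²] = 7.849/0.25 = 31.4.
- Divided by the Wilcoxon efficiency of 0.955: 31.4/0.955 = 32.9, rounded up to 33.
- The exact two-sided sign test at n = 33 has 81.9% power.

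The stated 33 is reproduced, and it is sized on post against pre within one person. No placebo term enters.

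**2. Does any listed test use the placebo cycle as comparator?** Section 7.4 gives the placebo and the crossover a purpose: to check diurnal variation and to let each volunteer serve as own control for each dose. Sections 9.3 and 9.4 contain no test that does this. Section 9.3 covers placebo cycles, but only as a further pre/post comparison.

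**3. Does anything mask draw time?** Section 8.5 covers treatment. Section 12.1 ties the code to participant and cycle. Section 12.2 points to a coding system that is not at the place cited. Under 8.7, fresh blood is processed within an hour, so arrival order would indicate draw time in the cell assays unless something is done about it. No masking is described.

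**4. Illustrative size.** Assumptions, none of them from the documents: no true change, normal paired differences, a constant reading shift of d SDs of the paired difference, and a two-sided test at 5% (the plan does not state sidedness). Rejection rates are simulated with 4,000 replicates. Where two figures are given at n = 40, they come from two runs.

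| Shift d | n = 33 | n = 40 |
|---|---|---|
| 0 | 4.3% | 4.7% |
| 0.1 | 7.8% | about 10% |
| 0.2 | 18.7% | 22-23% |
| 0.3 | 37.9% | 43-45% |

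Hand check for d = 0.2, n = 40: 0.2 × √40 × √0.955 = 1.236. Then 1.236 - 1.960 = -0.724, a tail of about 23%, which agrees.

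**5. Would comparing changes remove it?** Let b be the reading shift between pre-dose and post-dose samples. Change on a dose = true change on that dose + b. Change on placebo = true change on placebo + b. The difference between the two contains no b, provided b is the same in all cycles. The treatment blind is what makes that plausible.

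**The case against.** **Silence is not exposure.** A reader might infer that laboratory staff will see the draw time. The documents do not say so. Samples are coded in some unspecified way, the identifier in 12.1 is a participant identifier rather than a tube label, and the laboratory manual is cited but not supplied. This stands: the supportable statement is that no masking of draw time is described.

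**Direction.** A reader might describe the risk as a tendency to read post-dose samples higher throughout. That is wrong for the second secondary endpoint, where the hypothesis is a decrease in activation. The bias of concern is toward the hypothesis, and its sign differs by assay.

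**Counts of false findings.** A reader might multiply the rates in the table by 50 mediators and compare the result with the 2-3 false positives the plan expects. That requires the same shift in all 50, in an assay with internal standards where discretion is narrower than in gating. It also ignores the functional filter. The documents support no such count.

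**The placebo cycle would show it.** It might, since a draw-time bias would also appear after placebo. A shift common to all doses would also cancel when doses are ranked by size of change. But 9.3 and 9.4 give no rule for discounting a change that also occurs on placebo, so the declared tests remain exposed.

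**The study is exploratory.** The synopsis says so, and that limits the harm. Section 9.3 still uses these readings to choose the dose and time for future trials.

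**Conclusion.** The point holds in a limited form. The stated blind covers treatment, the tested contrast is post-dose against pre-dose, and no masking of draw time is described. The treatment blind therefore does not protect the planned tests from a reading bias toward the hypothesis. The exposure is greater for cytometry gating than for LC-MS/MS.

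The size is unknown. The figures of about 10%, 22-23% and 43-45% per affected test at n = 40 follow only from the assumed shifts of 0.1, 0.2 and 0.3 SD. They show how sensitive the test is and do not estimate what will happen. The documents do not support a claim that staff will be unmasked, that every mediator would be affected, or that the results would be invalid. This is an inexpensive bias control that should be settled before any sample is read.

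**What to change.** **In 8.5 and 8.7, state that:**
- stored plasma aliquots (40 × 4 × 5 = 800) carry random numbers that hide cycle and draw time during LC-MS/MS and peak review;
- each participant's 4 × 5 = 20 samples stay in one batch, which fits the planned 20-24, and are run in random order;
- cytometry files are saved and gated under random names;
- the link file is held outside the laboratory and opened only after the readings are locked.

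Section 12.2 should then say who holds this link file, and its reference to 14.3 should be corrected. If the laboratory manual already covers these steps, a sentence and a citation in 8.5 suffice.

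**In 9.4, add** a within-person comparison of change from baseline on each dose against change on placebo at the same draw time. This cancels any draw-time reading bias common to all cycles.

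**Cost.** Relabelling, a link file, and holding each participant's plasma until the last cycle; -80°C storage is already planned. Fresh cell assays cannot be masked at acquisition, only at gating. The added comparison was not part of the calculation that gave 33. If changes in two cycles were uncorrelated with equal variance (an assumption), the SD of their difference would be √2 = 1.41 times that of one change, so its power should be worked out separately.
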